1. STUDY OBJECTIVES

1.1 Primary Objective

1. To refine an existing compassion meditation protocol for PTSD by evaluating participants' reactions to the intervention components and refining the practices to maximize engagement and induction of cognitive/emotional states that are most likely to counteract PTSD.
2. To evaluate the acceptability of and refine a likely future control condition (i.e., relaxation).
3. To evaluate the feasibility of conducting compassion meditation as an intervention for PTSD.
4. To establish preliminary estimates of effect size and other parameters to inform future efficacy studies of compassion meditation.

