9. STATISTICAL CONSIDERATIONS

9.1 General Design Issues

This project is a feasibility and proof of concept study of compassion meditation (CM) for Veterans with posttraumatic stress disorder (PTSD; $N \approx 100$). Phase 1 ($N \approx 60$, nonrandomized, Protocol Refinement, will consist of up to 4 CM and 2 Relaxation groups with 6-12 participants in each group. Iterative refinement of the treatment protocols will be done based on quantitative and qualitative data from participants. Phase 2 ($N \approx 40$), Pilot Evaluation is a randomized controlled study with 4 groups (2 CM and 2 relaxation groups, 6-12 in each group) to examine the feasibility of a randomized trial and to estimate response to CM. The study is not hypothesis driven, but rather developmental in nature.

The primary outcome measures in Phase 1 (see section 6.2) are related to refinement of the intervention, i.e., participants' behavior and reactions to the material and change in processes that are believed to be modified by CM (i.e., positive emotion, social connectedness, self-compassion). The primary outcome measures in Phase 2 (refer to section 6.2) are related to estimating the amount of change in symptomatology, functioning and psychological processes thought to be associated with CM.

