9.5 Outcomes

9.5.1 Primary Outcome

The primary outcomes of Phase 1 are participant reactions to the group (credibility, satisfaction, attendance, practice compliance, and weekly qualitative and quantitative feedback) as well as variables that reflect changes that are expected with practice of CM (positive emotion, social connectedness, self compassion). These includes: Client Satisfaction Questionnaire, credibility score, modified Differential Emotions Scale, time spent in and reactions to daily practice, reactions to group, short form of the Self Compassion Scale and Social Connectedness Scale. Refer to section 6.2 for the schedule of administration and descriptions of measures.

The primary outcome of Phase 2 is the CAPS-5, which quantifies PTSD symptomatology.

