For quantitative data, descriptive statistics will be used to summarize the variables as well as to detect outliers and data entry errors. When applicable, normality of the distribution will be examined for outcome variables with a normal probability plot. HRV measures will be generated from heart rate data per the recommendations of the Task Force of the European Society of Cardiology and the North American Society of Pacing and Electrophysiology (Task Force, 1996). Chi- squares and Analysis of Variance will be used to assess the effectiveness of the randomization procedures by comparing participants in each treatment condition on baseline variables. Although there are important limitations associated with the analysis of our phase 2 data, we do propose to conduct limited statistical analyses. First, keeping in mind the theoretical and practical issues reviewed above, all analyses will be considered preliminary. We will calculate an estimated effect size for our primary outcome, though it will be interpreted with caution, and in the context of the 95% confidence interval that surrounds it. It will also be interpreted within the context of other important information such as the clinical significance of study findings, and existing data from prior relevant research studies.

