Primary analyses will assess whether CM is superior to Relaxation. The two groups will be compared on CAPS, BSI, SDS and Philadelphia Mindfulness Scale using analysis of variance. We are also particularly interested in evaluation of patterns of missing data, dropout rates, distributional properties of variables, and correlations among measures. Missing data will be examined to assess randomness. The pattern of missing data will be examined according to the procedure recommended by Little and Rubin (1987), which includes comparing group differences in the primary outcomes of subjects with versus without missing data. We will test whether the drop-outs are random or systematic by comparing the drop-outs with the study completers on the baseline data. An absence of significant differences would support the random nature of drop- outs. Dropout rate will be compared between the groups using chi-square analysis. Given the limited sample size, multiple linear regression may be used carefully to examine whether group assignment predicts PTSD symptom severity at the follow-up assessment while controlling for initial values. Other potential covariates will include baseline demographic or clinical variables (e.g., concomitant medication use) that are not equivalent between the two treatment groups. Effect size for the difference between groups will be calculated according to procedures described by Cohen (1988). We will also explore the effect of patterns of missing data using Mixed Effects models (random regression models). We will perform sensitivity analyses for the impact that potentially informative missing data and dropout may have on the analyses. The mixed effects framework is robust with respect to drop-out and missing data, unless the drop-out mechanism or cause of missing is informative. We will use pattern-mixture models to assess if there is bias due to drop out or missing data.

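### Phase 2 names an ANOVA with no stated baseline term as its primary comparison, leaves baseline adjustment optional, and ties the CAPS-5 effect size and 95% CI to no model

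*Combined protocol and SAP*

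**What the plan says.** Section 9.5.1 fixes the endpoint: "The primary outcome of Phase 2 is the CAPS-5, which quantifies PTSD symptomatology". Section 9.6 then describes the primary analyses as a test of whether CM is superior to relaxation, and gives the method: "The two groups will be compared on CAPS, BSI, SDS and Philadelphia Mindfulness Scale using analysis of variance". It states no dependent variable (post-treatment score or change), time factor or baseline covariate. Section 9.1 says that the Phase 2 primary outcome measures "are related to estimating the amount of change in symptomatology, functioning and psychological processes thought to be associated with CM". That fits a change score but does not settle the matter.

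Baseline values enter once, later in Section 9.6: "multiple linear regression may be used carefully to examine whether group assignment predicts PTSD symptom severity at the follow-up assessment", with the initial value held constant. The verb makes this optional, and the only outcome covered is PTSD severity. Further covariates are picked by what the data show: "Other potential covariates will include baseline demographic or clinical variables (e.g., concomitant medication use) that are not equivalent between the two treatment groups".

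On the effect size, Section 9.6 says "We will calculate an estimated effect size for our primary outcome, though it will be interpreted with caution" and adds that it will be read alongside its 95% confidence interval. Later it says "Effect size for the difference between groups will be calculated according to procedures described" in a cited 1988 reference. Neither sentence says whether the estimate comes from the ANOVA, the regression or the mixed model, or from post, change or adjusted scores. The mixed and pattern-mixture models are introduced only to explore missing data and dropout.

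The Phase 2 table in Section 6.1, with Sections 6.2.2 and 6.2.5, schedules the CAPS-5, BSI, SDS and PHLMS (the Philadelphia Mindfulness Scale) at both baseline and post-treatment.

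**The concern.** Section 1.1 lists among the primary objectives "To establish preliminary estimates of effect size and other parameters to inform future efficacy studies of compassion meditation". The CAPS-5 estimate and its interval are therefore a main product of Phase 2, yet the plan does not determine them. Two analysts could follow Section 9.6 faithfully, one using post-treatment scores and the other change scores, and report different effects from the same data. Each could then decide, after seeing the results, whether to run the adjusted regression and which unbalanced covariates to put in it.

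Precision is also at stake. In a trial of about 40 people the interval will be wide under any model. A post-score ANOVA leaves the variance that baseline severity explains in the error term, and leaves any chance baseline difference between arms in the estimate. Bias is not at stake: averaged over randomisations, the unadjusted comparison is unbiased. What is lost is precision, protection from chance imbalance, and a model fixed before the data are seen.

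**Working it through.** **Inputs from the protocol.** Phase 2 has about 40 participants in four groups of 6 to 12, two groups per arm (Section 9.2). That gives 4 × 6 = 24 to 4 × 12 = 48 in total, or 12 to 24 per arm, with 20 per arm at the planned size. The confidence level is 95% (Section 9.6). The protocol gives no SD, power or precision figure, so there is no figure of its own to reproduce.

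**Assumptions.** The correlation r between baseline and post-treatment CAPS-5 is not in the documents. I take r = 0.3, 0.5 and 0.7, and 0.2 as a low case. Outcomes are treated as independent, with equal SDs at both times and no dropout. Results are in SD units; n is the number per arm and N = 2n.

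**Formulas for the 95% half-width**

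- Post-score ANOVA: t(0.975, N−2) × √(2/n)
- Change-score ANOVA: t(0.975, N−2) × √[(2/n) × 2(1−r)]
- Baseline-adjusted model: t(0.975, N−3) × √[(2/n)(1−r²)(N−3)/(N−4)]. The last factor is the cost of estimating the slope.

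**At n = 20, N = 40**

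The post-score half-width is 2.024 × √0.1 = 2.024 × 0.316 = 0.640. The adjusted half-width at r = 0.5 is 2.026 × √(0.1 × 0.75 × 37/36) = 0.563. The equivalent unadjusted N is 40 / [(1−r²) × 37/36].

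| r | Post-score | Change-score | Adjusted | Equivalent unadjusted N |
|---|---|---|---|---|
| 0.2 | 0.640 | 0.810 | 0.636 | 40.5 |
| 0.3 | 0.640 | 0.757 | 0.620 | 42.8 |
| 0.5 | 0.640 | 0.640 | 0.563 | 51.9 |
| 0.7 | 0.640 | 0.496 | 0.464 | 76.3 |

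**Across the planned range, at r = 0.5.** The post-score half-width of 0.847 becomes 0.753 with adjustment at 12 per arm. At 24 per arm, 0.581 becomes 0.509. At 12 per arm and r = 0.2, adjustment is marginally worse (0.852 against 0.847).

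**What the unstated dependent variable can do.** On the same data, the post-score estimate minus the change-score estimate equals the difference in baseline means. Its SD at 20 per arm is √(2/20) = 0.316. The probability that it exceeds 0.3 SD in either direction is 2 × [1 − Φ(0.3/0.316)] = 2 × [1 − Φ(0.949)] = 0.343, whatever r is.

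**What adopting the adjusted model would move.** I simulated 100,000 trials of 20 per arm. The adjusted estimate differs from the post-score estimate by more than 0.3 SD in about 2%, 7% and 17% of trials at r = 0.3, 0.5 and 0.7. It differs from the change-score estimate by that much in about 18%, 7% and 1%.

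**The case against.** The strongest reply is that this is a pilot that does not overclaim. Section 9.1 describes the study as developmental. Section 9.6 says that effect-size estimation is not the main focus, warns about the large standard error of pilot estimates, and labels all analyses preliminary. Even the adjusted interval at r = 0.5, about ±0.56 SD, is too wide to settle superiority. This stands, and it limits the consequence. It does not remove the point, because effect-size estimation is still a primary objective and a superiority comparison is still called primary.

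A second reply is that the remedy is already there for PTSD severity, with the small sample given as the reason for caution. That is partly right: for CAPS-5 the edit is small. But the regression remains optional, sits beside an ANOVA labelled primary, and does not extend to the other three scales. The small sample is a weak reason to hold back, since one covariate costs one error degree of freedom plus a small estimation cost, and both are in the figures above.

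A third is that a group-by-time repeated-measures ANOVA also fits the wording and would include baseline. With two time points its interaction test is the change-score test, so the change-score column already covers it.

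A fourth is that a reference is cited for the effect size. The protocol still does not say which score or model feeds that calculation.

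Two limits stand in full. The gain depends on an undocumented r and nearly vanishes at about 0.2. And the 34% figure measures the gap between two readings of the plan; moving to the adjusted model usually shifts the estimate less. The 0.3 SD threshold is illustrative and has no source in the documents.

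**Conclusion.** The concern holds. The primary Phase 2 comparison has no stated baseline term, adjustment is optional and confined to PTSD severity, and the CAPS-5 effect size and interval are attached to no model. The textual gap is clear. The size of the benefit is less certain: under the assumptions above, the half-width at 20 per arm shrinks by 0.02 to 0.18 SD relative to a post-score ANOVA as r runs from 0.3 to 0.7 (0.640 − 0.620 to 0.640 − 0.464). The value of fixing one model in advance does not depend on r.

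This is a change that should be made rather than a fatal flaw. All the half-widths ignore dropout and clustering by therapy group. They do not apply to an analysis at group level, where two groups per arm leave 2 degrees of freedom.

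**What to change.** In Section 9.6, name the primary Phase 2 analysis as a linear model of post-treatment CAPS-5 on arm and baseline CAPS-5, and state that the effect size and 95% confidence interval come from that model. Use the same form for BSI, SDS and PHLMS, each with its own baseline. Drop the selection of covariates by observed imbalance, and name any further covariate in advance.

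The cost is a wording change. No visit, measure or participant is added. Clustering within therapy groups is a separate matter that this change does not resolve.

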10. DATA COLLECTION AND QUALITY ASSURANCE

10.1 Data Collection Forms

Indicate how information will be collected for each participant and by whom. For example if a blinded observer will perform outcome assessments, state who this person will be. Describe methods for maintaining confidentiality of participant records. Identify any data that will be

recorded directly on the CRFs (i.e. no prior written or electronic record of data) as this will be considered source data. (ICH Guidelines, E6.4.9)

Trained assessors will administer the measures for this study. Data collected in this project includes a structured interview and self-report measures about mental health symptoms, including alcohol use, quality of life, functioning and response to meditation practice. Designated staff members will have access to individually identifiable private information about human subjects. All such staff will receive training in proper handling of research data, and systems will be put in place to maintain subject confidentiality to the greatest extent possible. For example, paper data will be stored in locked file cabinets in locked rooms. Subject names (including consent forms and the key associating names with subject numbers) and contact information will be stored separately from other study data, which will be identified using a subject ID number. Electronic data will be stored on a password-protected secure server.

10.2 Data Management

Data management will be supervised by the study statistician, [name]. He has more than 28 years experience in data management and analysis. The computer systems to be used (VA and Veterans Medical Research Foundation) are HIPAA compliant and housed in locked rooms, accessible only to authorized personnel and employees. All subjects are assigned a unique ID number. The patient names are never used in conjunction with the unique clinic ID number. The single name-to-ID relational file is kept in an encrypted form electronically and in a locked filing cabinet physically. Data will be collected on paper forms and entered into an already existing data management system. Prior to inferential analyses, data will be examined for missing values and statistical outliers. All statistical transfer routines are inherently secure via their operating platform and they contain no patient names or personal data.

10.3 Quality Assurance

10.3.1 Training

Assessment. The assessor in Phase 2 will be a doctoral-level psychologist with familiarity with diagnostic interviewing. [name] will provide study-specific training prior to conducting interviews. Training for the MINI will include a didactics on the interview, including the suicidality/homicidality assessment, and administration of practice interviews with a mock patient. Training in the CAPS will include review of training materials, observation of CAPS administration, and diagnostic matching on three CAPS interviews. To establish matching, [name] will co-rate the training interviews conducted by the assessor. A match occurs when the assessor and [name] agree on the diagnosis and are within 2 points of severity (frequency + intensity) on all of the symptom clusters (PTSD criteria B, C, and D). Each assessor will be considered trained on CAPS when he or she matches [name] on three interviews (this requirement may be reduced with documentation of prior rigorous CAPS training). If the assessor does not match on three interviews after five attempts, [name] will provide additional training or the assessor will be replaced. [name] will supervise the assessor's interviews throughout the study, and all interviews will be audio-recorded in case detailed review of an interview is needed. We will follow standard procedure for ensuring inter-rater reliability over time. Each assessor's score will be compared to the [name] "gold standard" rating. Intra-class correlation coefficients (ICCs) of each assessor must be .90 or higher. If the ICC falls below .90, retraining will be done. Reliability will be re-established annually or more frequently if requested by the project PI or the study statistician.

Interventions.

We will follow accepted standards (Perepletchikova & Kazdin, 2005) in establishing and assessing the integrity and fidelity of the interventions. This includes: a) treatment manuals with weekly objectives, outcomes, and agendas, b) clinician training, and c) ongoing evaluation of treatment integrity through audio-rating of therapy sessions and supervision.

The CM protocol will be taught using the Emory Intensive Teacher Training Program. The program is designed to help potential teachers explore effective contemplative pedagogy, understand and adapt to the needs of various populations, and deepen their personal meditation practice. The prerequisites for this training are having a regular meditation practice of at least one year and having attended at least one teacher-led residential retreat. The first portion of the training (taught as a week-long or two-weekend intensive) involves an introduction to the key concepts, skills, and practices, including understanding the theory and practice of CM, learning how CM differs from other meditation-based programs and recognizing the rationale and significance of teaching secularized meditation programs. The second portion of the training, which is a retreat, affords participants an opportunity to deepen their practice and experience with CM. Participants are expected to continue deepening their personal meditation practice on their own after the intensive training. The third training component involved supervised administration of the protocol. A supervisor from Emory will watch a video- recording of every class and provide feedback to the therapist prior to the next class.

The relaxation protocol will be conducted following the Taylor manual. [name] will review recordings of every session to assure adherence to the protocol. A fidelity measure will be developed for each intervention at the end of the refinement phase and will be evaluated in the pilot phase. To identify problems early, the Emory group will listen to audiotapes of each session. Corrective feedback will be provided as needed in weekly supervision. The participant evaluation method of quality assurance, which involves asking each participant to complete a brief checklist that queries the content of their session, will be employed as well.

10.3.2 Quality Control Committee

Data monitoring will be the responsibility of [name].

10.3.3 Metrics

Outcome measures will be checked for missing and impossible values as well as for internal inconsistencies.

10.3.4 Protocol Deviations

A protocol deviation or violation is any change, divergence, or departure from the study design or procedures of a research protocol. Investigators are required to conduct their research according to the plans reviewed and approved by the IRB. Staff will be trained to avoid protocol deviations to the extent possible. Instances where this does not occur, either inadvertently due to circumstances beyond the investigator's control or due to errors of omission or commission by research project staff, will be reported.

Protocol deviations will be recorded and maintained by the study coordinator on the Protocol Deviation Log and reviewed by [name].

Protocol deviations that do not affect participant safety or data integrity will be reported to the VASHS IRB at continuing review. Any protocol deviation resulting in harm or risk to the participant must be reported within ten business days to the VASDHS IRB using the VASDHS Human Research Protections Program form REPORT OF UNANTICIPATED PROBLEM INVOLVING RISK TO SUBJECT OR OTHERS (dated 7/9/12).

10.3.5 Monitoring

The VA San Diego conducts annual reviews of consent forms to assure compliance. Research assistants and therapists will be trained to review all instruments for completeness before the participant leaves the appointment. [name] will review the data set for completeness at the end of each group cycle.

11. PARTICIPANT RIGHTS AND CONFIDENTIALITY

11.1 Institutional Review Board (IRB) Review

This protocol and the informed consent document and any subsequent modifications will be reviewed and approved by the VA San Diego IRB and R&D Committee.

11.2 Informed Consent Forms

Consenting will take place at the Oceanside VA clinic with a trained assessor/study coordinator in a private room and the participant will be given ample time to read the consent form and ask questions. At the first visit, prior to initiation of any study- related procedures, subjects will give their written consent to participate in the study after having been informed about the nature and purpose of the study, participation/termination conditions, risks, and potential benefits. Informed consent is a process that is initiated prior to the individual's agreeing to participate in the study and continuing throughout the individual's study participation. Upon reviewing the document, the assessor will explain the research study to the participant and answer any questions that may arise. Extensive discussion of risks and possible benefits of this therapy will be provided to the participants as needed. The investigator will explain study procedures, including the variable length of follow-up in this study, and let the participant know how many follow-up assessments he/she will be asked to complete. The participants will sign the informed consent document prior to any procedures being done specifically for the study. The participants may withdraw consent at any time throughout the course of the trial. A copy of the informed consent document will be given to the participants for their records. The rights and welfare of the participants will be protected by emphasizing to them that the quality of their medical care will not be adversely affected if they decline to participate in this study. VA subjects will consent to the audio-video recording using VA form 10-3203. Decisional capacity will be assessed based on the interviewer's judgment during the dialog that takes place during recruitment and screening. In addition, the participant participates in a comprehensive psychological assessment as part of the screening including questions about traumatic brain injury. We also anticipate that the clinician referral will screen out anyone with severe cognitive problems. Participants with questionable decisional capacity will be excluded from the study.

